## 10.3 Statistical analysis plan

All statistical analyses will be undertaken according to a predefined detailed statistical analysis plan (SAP) agreed in advance with the trial management group, trial steering committee.

Baseline sociodemographic and outcome variables will be reported and compared descriptively by treatment arm.

The primary analysis will be conducted on an intention-to-treat basis comparing both primary and secondary outcomes between treatment and control groups in those with complete data at week 104 follow up. Linear regression models will adjust for baseline score and stratification variables.

Secondary analyses will include: between group comparisons at all follow up time points using mixed model repeated measures approach; between group comparison of primary and secondary outcomes at primary outcome time point based on imputed outcome data (using multiple imputation models based on an assumption that data is missing at random); per-protocol analysis using an estimated complier average causal effects analysis (CACE) of the primary outcome at the primary outcome follow-up data; and an exploratory assessment of subgroup effects using interaction terms based on subgroup effects. Prior to analysis and to be defined in the SAP, the trial management group will pre specify the per-protocol definition and subgroup.

All analyses will be undertaken by a statistician blinded to group allocation. Results will be reported means and 95% CIs.

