### 7.7 Trial assessments

Assessments will be conducted at baseline, 26, 52, and 104 weeks. Participants will receive weekly automated emails notifying them that assessments are available to complete until they are completed or no longer available. The assessments will become available for completion two weeks before the assessment point and remain open for completion during the week of the assessment point and a further five weeks, making them available for eight weeks in total. Missing data or late data will be accounted for within the analysis plan.

Assessments will follow the set online assessment protocol described below.

1. scale Trail-making B (primary outcome measure)
2. PROTECT Cognitive Tests: Switching Stroop Test, Baddeley Grammatical Reasoning , Self-ordered Search, Digit Span, and Paired Associate Learning Tasks (secondary outcome measures)
3. Instrumental Activities of Daily Living
4. EQ5D measure of health and wellbeing
5. Mild Behaviour Impairment Scale

An anonymous survey will be completed at the end of the study to provide a process measure and to capture participant experience.

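### The primary analysis is called intention-to-treat but is restricted to week-104 completers, while the planned analyses that use interim data are only secondary

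*Protocol*

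**What the plan says.** Section 10.3 (Statistical analysis plan) of the protocol fixes the primary analysis in two sentences. The first states "The primary analysis will be conducted on an intention-to-treat basis" and goes on to define it as "comparing both primary and secondary outcomes between treatment and control groups in those with complete data at week 104 follow up". The second gives the model: "Linear regression models will adjust for baseline score and stratification variables".

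The same section then lists two analyses that deal with missing outcomes differently, both as secondary. One is the repeated-measures comparison: "Secondary analyses will include: between group comparisons at all follow up time points using mixed model repeated measures approach". The other is a comparison at the primary time point on imputed outcomes, "using multiple imputation models based on an assumption that data is missing at random".

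Section 7.7 sets the schedule: "Assessments will be conducted at baseline, 26, 52, and 104 weeks". It also promises that missing or late data will be dealt with in the analysis plan. Section 3.7 makes 24 months the primary endpoint. Section 10.1 assumes 20% drop-out from 584 participants.

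Section 7.8 has a withdrawal route under loss of capacity. A participant more than one standard deviation below age-matched norms on two cognitive tests at two consecutive assessments is reviewed by a study doctor, and is withdrawn if the concern is judged valid. The withdrawal procedure says that anonymised data are kept. It does not say that outcomes are collected afterwards.

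**The concern.** Intention-to-treat means analysing all randomised participants in the arm to which they were allocated. Completing the two-year assessment is an event after randomisation, so selecting on it gives a completers analysis whatever it is called. Nothing elsewhere in the protocol resolves this. Leaving detail to a separate SAP does not help either, because the protocol itself already fixes the primary set.

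The choice also rests on an assumption that the design weakens. A week-104 regression on baseline and strata is unbiased only if, given arm and those covariates, the chance of a missing week-104 value does not depend on how the participant was doing during follow-up. Section 7.8 allows such a dependence. If the supplement works across the tests, more placebo participants would reach the flag and the remaining completers would differ less between arms. The week-26 and week-52 scores carry much of the information behind that selection. The primary model ignores them, whereas the two secondary analyses can use them. What is at stake is the headline estimate and the accuracy of the label under which it is reported.

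**Working it through.** **Inputs from the protocol.** Effect size 0.3, two-sided 5% level, 90% power, 234 per group, 20% drop-out, 584 in total (section 10.1); visits at weeks 26, 52 and 104 (section 7.7). Correlations, the timing of drop-out and the rate of score-linked withdrawal are not given, so those below are assumptions.

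**1. The plan's own figures.** The normal-approximation formula for two means at 0.3 SD gives 234 per group, with power 90.1%. Allowing for drop-out, 234 / 0.8 = 292.5, rounded up to 293. Both reproduce. (2 × 293 = 586 against the stated 584 is trivial and has no bearing here.)

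**2. Who is left out.** 584 × 0.20 = 116.8, about 117 excluded; 584 × 0.80 = 467.2, about 234 per arm analysed. This is the number the sample size was built on, so the restriction does not take power below 90%. If all 292 per arm were observed, power would be 95.2%. That is an upper bound for any analysis that recovers part of the missing information.

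**3. Precision gained from weeks 26 and 52.** Assume an equal correlation ρ between visits.
- Given baseline, the correlation between two follow-up visits is r = ρ/(1+ρ): 0.375 for ρ = 0.6 and 0.444 for ρ = 0.8.
- The share of week-104 variance explained by one interim visit is R1 = r² = 0.141 to 0.198. By both it is R2 = 2r²/(1+r) = 0.205 to 0.274.
- With fractions n1, n2 and 0.8 of participants observed at weeks 26, 52 and 104, the variance relative to completers is [(1−R2)/0.8 + (R2−R1)/n2 + R1/n1] / (1/0.8).

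| Timing of the 20% loss | n1, n2 | Variance ratio | Gain |
|---|---|---|---|
| All after week 52 | 1, 1 | 0.959 to 0.945 | 4.1 to 5.5% |
| Even over the three visits | 0.933, 0.867 | 0.975 to 0.966 | 2.5 to 3.4% |
| Half before week 26, a quarter in each later interval | 0.90, 0.85 | 0.981 to 0.974 | 1.9 to 2.6% |

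The gain is about 2 to 6%.

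**4. Bias, simple bound.** If a fraction d of an arm drops out and the drop-outs score g SD worse than completers, the completers' mean exceeds the arm's mean by d × g. The bias in the contrast is d₁g₁ − d₀g₀ (active minus placebo, benefit positive).
- Equal drop-out and equal deficit: 0.
- 15% against 25%, g = 0.25 to 0.5: (0.15 − 0.25) × g = −0.025 to −0.05.
- 20% in both arms, deficits differing by 0.3 SD: 0.20 × 0.3 = 0.06 in size, a fifth of the 0.3 target.

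**5. Bias under the section 7.8 rule.** Simulations used six tests, retest correlation around 0.6 to 0.7, a true effect of 0.30, no outcomes after withdrawal, and several assumed correlation structures. With half of flagged participants withdrawn, the completers regression gave about 0.28 to 0.31. Where total withdrawals stayed within about the planned 20%, it gave about 0.26 to 0.30. A repeated-measures model on Trails-B, or imputation using the interim tests, came closer to 0.30. Under ordinary drop-out moderately related to the week-52 score, the completers estimate was 0.29 to 0.30.

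**The case against.** The strongest reply is that the protocol already pre-specifies both missing-at-random analyses, so readers will see them whichever is called primary. Complete-case regression with baseline adjustment is valid when missingness depends only on arm, baseline and strata, and under ordinary drop-out the bias is close to nothing. All this is true, and it is why the point is not graded higher. It does not remove the contradiction in section 10.3, nor the reason section 7.8 gives to doubt the assumption.

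Several stronger readings are tempting, and the protocol does not support them:
- *Low scores remove people automatically.* Section 7.8 makes them a trigger for doctor review; withdrawal follows only if the concern is upheld.
- *The estimate could fall to about 0.22.* In the simulations that needed a cohort averaging 1 SD below norms, a full 0.30 gain on every test from week 26, and withdrawal of everyone flagged. That removes more than half the trial, against a planned 20% drop-out.
- *Complete data means complete on every outcome*, so that people who finish only Trails-B are lost. The amendment history says Trails-B was chosen partly so that more data would enter the primary analysis, which points to completeness judged outcome by outcome.
- *Power is lost.* The 234 per group is already the completer number.
- *The mixed model keeps everyone randomised.* A standard one keeps those with at least one post-baseline value of the outcome; imputation can keep all.

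Which variables enter the imputation model, and the form of any shift analysis, are ordinary SAP matters and are not raised as omissions.

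**Conclusion.** The point stands as a should-fix. Section 10.3 gives the intention-to-treat name to a completers analysis that would leave out about 117 of 584 participants at the planned drop-out. It also makes primary the one planned approach that cannot use follow-up scores to account for who is missing.

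The size of the harm is uncertain and probably modest: about 0.26 to 0.30 for a true 0.30 in plausible scenarios, towards the null under score-linked withdrawal, and lower only under extreme assumptions. The precision forgone is about 2 to 6% of the variance, depending on when people drop out and on assumed correlations of 0.6 to 0.8. The bias figures rest on two further assumptions: that no outcomes are collected after withdrawal, on which the protocol is silent, and how many flagged participants are in fact withdrawn, which it does not give. A reader might infer that the trial's result would be seriously distorted or underpowered; the documents support neither.

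**What to change.** In section 10.3, make one of the two missing-at-random analyses already planned the primary analysis of the week-104 contrast, with participants in their allocated arm. Either would serve:

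- the mixed model over weeks 26, 52 and 104, including all randomised participants with any post-baseline value of that outcome; or
- multiple imputation that uses the interim scores, including all randomised participants.

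State the analysed set in those terms instead of applying the intention-to-treat label to completers. Keep the week-104 complete-case regression as a sensitivity analysis, ideally beside one that departs from missing at random.

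The cost is one paragraph in section 10.3, with matching text in the SAP, and slightly more modelling work. No extra data, visits or participants are needed. The change should be settled before unblinded outcome data are seen.

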## 11 DATA MANAGEMENT

### 11.1 Data collection tools and source document identification

All data will be collected online via the PROTECT platform, which conforms to all UK GDPR regulations and the Data Protection Act 2018. Trial data will be stored in a bespoke fully encrypted trial database in a linked anonymised format. The database will be stored online on University of Exeter servers and in cloud-based storage provided by Microsoft Azure (UK site). Full details are available in the PROTECT study specification documentation.

Some of the participants' personally identifiable (PII) and some sensitive data will be manually entered into REDCap Cloud for randomisation and stratification for treatment allocation. Password protected Excel spreadsheets stored within the secure trial management files on the University of Exeter shared drives will be used to manage dispensing, log Adverse Events and record the outcome of the compliance telephone call.

### 11.3 Access to Data

Direct access will be granted to authorised representatives from the Sponsor, host institution and the regulatory authorities to permit trial-related monitoring, audits and inspections- in line with participant consent.

### 11.4 Data Recording and Record Keeping

All data collected on the PROTECT platform for VitaMIND will be stored in Microsoft Azure UK region SQL databases. Personally identifiable data will remain in the PROTECT cohort database using a unique and independent ID and held on a separate database from the non-identifiable trial results data. There will be no means of linking the two data sets via the databases. Backup instances of the data will be created daily.

Only approved database developers will have access to personally identifiable data through the electronic database. A combination of the management portal and REDCap Cloud will give the approved administration team access to the information required to liaise with participants, extract randomisation information for dispensing and follow up any Serious Adverse Events. The administration portal and REDCap Cloud require username and password login.

Data may also be downloaded from the data portal and stored alongside other study documents in password-protected databases, which only the study team will have access to. Any paper records (copies and/or original documents) deriving from or belonging to the study will be kept in a locked filing cabinet, in a locked room, in a secure building the University of Exeter Medical School. Where applicable, these records will be pseudonymised by physically obscuring any PII and replacing it with the participant's Results ID.

The anonymised dataset will be retained for 10 years after the end of the trial. Where data is part of the overall PROTECT dataset this will be retained for the length of the PROTECT longitudinal study. Data will be made available for reuse based on the University of Exeter's Open Research Exeter (ORE) policy for open access. Investigators wishing to access study data will complete a data access application. This is required since some trial data is also held as PROTECT study data.

## 13 ETHICAL AND REGULATORY CONSIDERATIONS

### 13.1 Declaration of Helsinki

The Investigator will ensure that this study is conducted in accordance with the principles of the WMA Declaration of Helsinki – Ethical principles for medical research involving human subjects.

### 13.2 Guidelines for Good Clinical Practice

The Investigator will ensure that this study is conducted in accordance with relevant regulations and with Good Clinical Practice.

### 13.3 Approvals

This trial is subject to full NHS REC and HRA review. Substantial amendments that require review by REC will not be implemented until the REC grants a favourable opinion for the trial. All documentation relating to ethics and approvals will be retained in the Trial Master File/Investigator Site File. An annual progress report (APR) will be submitted to the REC within 30 days of the anniversary date on which the favourable opinion was given, and annually until the trial is declared ended

It is the Chief Investigator's responsibility to produce the annual reports as required and to notify the REC and Sponsor of the end of the trial. If the trial is ended prematurely, the Chief Investigator will notify the REC and Sponsor, including the reasons for the premature termination. Within one year after the end of the trial, the Chief Investigator will submit a final report with the results, including any publications/abstracts, to the REC

### 13.4 Reporting

The CI shall submit once a year throughout the study, or on request, an Annual Progress report to the REC Committee, HRA (where required), host organisation and Sponsor. In addition, an End of Study notification and final report will be submitted to the same parties.

### 13.5 Participant Confidentiality

Data protection processes will be fully compliant with the UK General Data Protection Regulation 2018 and Data Protection Act 2018. All investigators and staff will comply with UK GDPR with regards to the collection, storage, processing and disclosure of any personally identifiable information (PII) and will uphold the regulation's core principles.

All PII will be stored as per in a separate and encrypted participants database, stored on a cloud-based server provided by Microsoft Azure and held within the UK region. Unique participant IDs will be created for each participant, using an unrelated sequence of characters, and this will not be linked to the pseudo-anonymised results data held in a separate database.

Only approved database developers will have access to personally identifiable data through the master electronic database. A management portal will give the Chief Investigator, [name], and the delegated administration team, access to personal information where required for the trial. Access to PII will be limited to the administrator responsible for sending out trial capsules, welcome packs and blood test kits, and this role will occur in a secure room at the University of Exeter Medical School. To achieve this, the minimum required PII will be extracted from the participants database (name and address), access to a portal that requires authorised login from which an authorised member of staff can use the unique participant ID to look up the name and address held for the participant and print straight from the portal so no data leaves the database or is stored outside the database. PII may also be stored in password-protected databases located on University of Exeter shared drives, which only the study team at the University will have access to.

Access to PII outside of the master electronic database and management portal (i.e. paper copies and participant email correspondence to the PROTECT helpdesk) will be limited to the Chief Investigator and the delegated administration/ managerial team. PROTECT study clinicians may gain access to PII for the purpose of reviewing cognitive performance data (please see section 9.2).

In the event of a subject access request (SAR), the individual will be provided with the UoE Data Subject Request Form including the contact details for the designated Data Protection Officer and will be advised to submit their request in writing.

No PII data will be transferred to any other third party without written participant consent, and PII will not be included in any analysis files or study disseminations. PII will be stored for three years after the study has ended. It will then be destroyed. Pseudonymised and anonymised information will be kept indefinitely and up until the study objectives have been achieved. If the participant continues to be involved in the overall PROTECT host cohort their PII will be retained in the core PROTECT study participants database as per study protocols.

The data custodian for this trial is the Chief Investigator, [name] ([[contact]](mailto:[contact])).

### 13.6 Public and Patient Involvement

This study has benefitted from a number of PPI activities including consultation with the NIHR Peninsula Collaboration for Leadership in Applied Health Research and Care (PenCLAHRC) PPI Group, who prioritised the study, and a PPI workshop with volunteer carers hosted by Alzheimer's Society. The protocol has also been refined following consultation with a lay focus group. PPI will be delivered for this study through the existing lay advisory group for PROTECT, which is a group of older adults including carers and former carers of people with dementia. The group will meet at key points throughout

the study and will be consulted on major issues such as recruitment and retention strategies. Members of the PPI group will be invited to raise any discussion points with investigators, and a member of the group will be a permanent member of the Project Management Group to ensure full representation across the study. Where wider discussion with lay groups is deemed necessary the PPI group at the PenCLAHRC group, hosted at the University of Exeter, will be consulted and online channels available through the PROTECT study will be utilised.

### 13.5 Protocol compliance

Protocol compliance will be monitored by the Trial Coordinator and reviewed by the TMG. Deviations will be documented on the relevant forms and reported to the Chief Investigator and Sponsor immediately.

### 13.8 Financial and other competing interests for the chief investigator, PIs at each site and committee members for the overall trial management

None

### 13.9 Indemnity

Indemnity will be covered by the standard insurance cover produced by the University of Exeter as Sponsor and as detailed in separate documentation.

### 13.10 Amendments

Substantial amendments will be approved by the TMG prior to request for Sponsor sign off and subsequent submission to the REC and notification to the HRA Amendments Team. Non-substantial amendments will be signed off by the Sponsor prior to submission to the HRA Amendments Team. No amendment will be actioned until full approval has been confirmed from local sites supporting the trial. Amendments will be recorded in Appendix A.

### 13.12 Access to the final trial dataset

Access to the trial dataset will be restricted to the TMG members. Applications for access to the dataset will be considered on a case-by-case basis by the TMG. There are no specific terms set by the funder for data access.

## 16 APPENDIX A: AMENDMENTS HISTORY

Amendment No.	Protocol Version No.	Date issued	Author(s) of changes	Details of Changes made
1	4.0	10 th July 2019	[name]	Addition of REDCap Cloud to manage dispensing records; clarification of vitamin D deficiency level scale; removal of CogTrack cognitive tests; follow-up for missing participants
2	5.0	28 th Oct 2019	[name] / [name]	Broadening of eligibility criteria to include family history of

				dementia and/or subjective memory concerns; removed stratification of AACD, Assessment scheduling change following TMG; addition of memory clinics as recruitment channel; updated end of trial definition; updated a few inconsistencies in text resulting from changes made in previous amendment; clarification that baseline assessments will be done at registration, prior to tablets being sent
3	6.0	7 th Sept 2020	[name]	Aligning definition of AACD to more standard definition requiring performance of 1 standard deviation below the age matched norm on one or more PROTECT cognitive test; clarifying “online cognitive tests” refers to COGTRACK™ cognitive tests; addition of partner platforms such as Join Dementia Research for participant identification; mitigating against the risk of a COVID-19 lockdown by sending larger supply of tablets when government Covid-19 alert levels are 2 or higher; update key references section; update trial administrator due to staff change; aligning email assessment reminder schedule to existing scheduling rules on PROTECT platform to avoid confusing participants or sending too many reminders
4	7.0	9 Sept 2022	[name]	Added anonymous end-of-study survey as process measure
5	8.0	5 May 2023	[name]	Change length of trial to two years from three due to a review of the study design by the TMG which gave confidence in the primary outcome measure at 2

				
years, and the confirmation that power has already been achieved for the two-year outcome. In addition, ending at two years will reduce participant burden and avoid the need for further expenditure on study tablets.
 
Update to technical description to database to accurately reflect its design.
 
Change to primary outcome measure from one cognitive test measuring executive function (Grammatical Reasoning) to another cognitive test of executive function (Trails-B). Trails-B is a widely used test in Alzheimer’s research and because it is presented first in the online cognitive test battery, the completion rate is expected to be higher, allowing more data points to be included in the analysis of primary outcome measure.
 
Change to power calculation to reflect the amended executive function primary outcome measure

